4. SUBJECT SELECTION

4.1 Subject Inclusion Criteria

- Age 18-89 years.
- Willing and able to provide written informed consent.
- Willing and able to comply with study assessments for the full duration of the study.
- Diagnosis of dry eye disease based on the followings:
 - Symptoms of dry eye disease such as foreign body sensation, burning, stinging, light sensitivity for at least 6 months.
 - Two or more of the following objective signs:
 - Schirmer test with anesthesia <10 mm at 5 minutes [mean Schirmer between eyes.

- Tear break-up time (TBUT) of <10 seconds.
- Corneal fluorescein staining of 4 (NEI grading scheme, 0-15) in at least one eye
- Lissamine green staining of the nasal and temporal conjunctiva
 (NEI grading scheme, 0-18) in at least one eye
- Corneal dendritiform cell count by confocal microscopy of >=75/mm² (13 immune cells per image)
- In good stable overall health.

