4.2 Subject Exclusion Criteria

- Central corneal subbasal dendritic cell count by *in vivo* confocal microscopy of
 <75/mm² in both eyes
- Active ocular allergies
- Active allergies to steroids, aminoglycosides, or benzalkonium chloride (BAK)
- History of contact lens wear within 3 months before enrollment.
- Intraocular surgery or ocular laser surgery within 3 months before enrollment.
- History of ocular infection within 3 months before enrollment.
- History of topical or systemic steroid treatment within 1 month before enrollment. In case of topical steroid use, a wash-out period of 1 month is required.
- History of increased intraocular pressure after using topical steroids (steroid responsive)

- History of systemic immunosuppressive treatment within 1 month before enrollment.
- History of any change in the frequency of topical cyclosporine or oral tetracycline compounds (tetracycline, doxycycline, and minocycline) within 1 month before enrollment.
- Any condition (including language barrier) that precludes subject's ability to comply with study requirements including completion of study.

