7. STUDY PROCEDURES

7.1 Screening Procedures

Prospective participants, as defined by the inclusion/exclusion criteria, will be considered for entry into this study. Concurrent enrollment of subjects who are participants in other studies will be allowed based on the investigator's discretion.

During the consent process, study design and treatment regimen will be discussed with each subject. Written informed consent will be obtained before any study specific procedures are performed. However, standard of care clinical information (such as: medical history, TBUT, staining, and Schirmer's test) obtained during a subject's clinical visit within the previous 48 hours can be used during the screening visit to determine eligibility and as their baseline assessments. Additionally, standard of care IVCM images taken within a week of, or during, the subject's screening visit may be used to determine eligibility and as a baseline assessment.

The following evaluations and procedures will be performed for all subjects during the screening and baseline period:

- Written informed consent
- · Record of current ocular and systemic medications
- Record of significant medical/surgical history in the past 5 years
- · Record of demographic data, including date of birth, sex, and race/ethnicity
- Tear Break-up Time (TBUT)
- Eye examination (best corrected visual acuity, slit lamp biomicroscopy, applanation tonometry, funduscopy)
- · Corneal fluorescein staining
- · Conjunctival lissamine green staining

- · Schirmer's test with anesthesia
- · Central corneal in vivo confocal microscopy (IVCM)

Researchers will document type and frequency of artificial tear, ocular ointment, and other dry eye therapies use by the subject.

Subjects will start the study medication the first day after their screening visit, while continuing the use of their current medications.

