7.8 Schedule of Activities (Study Table)

Т	able1- Schedule	e of events ar	ıd procedu	res	
Visit#	1			2	3
Visit Description	Screening	Baseline	Day 1	Week 2	Week 6 (±
				(± 3 days)	1 week)
Obtain Informed Consent	X				
Inclusion/ exclusion criteria	X				
Medical and Ophthalmic History	X		START OF STUDY MEDICATION	X	X
Medication History	X		DICA		
BCVA	X		Y ME	X	X
OSDI		X	IUD	X	X
SANDE		X	OF S	X	X
TBUT	X		ART	X	X
Biomicroscopy	X		ST	X	X
Corneal staining	X			X	X
Schirmer with anesthesia	X			X	X
Conjunctival staining	X			X	X

Intraocular Pressure	X		X	X
Funduscopy	X		X	X
In vivo confocal	X		X	X
microscopy				
Concommitant			X	X
medications				
Compliance and	X	X	X	X
adverse events check				

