10. STATISTICAL METHODS/DATA ANALYSIS

10.1 Primary endpoint(s) or outcome measure(s)

In Vivo Confocal Microscopy

- > Superficial corneal epithelial cells: Density, size, and hypereflectivity
- > Corneal subbasal immune dendritiform cells: Density, size, and cell field
- > Corneal subbasal nerves: Number and length of the main nerves and the branches

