10.5 Effectiveness Analysis

For efficacy variables and any other variables except for safety, all subjects will be analyzed with the treatment to which they were randomized (the intent-to-treat population). Subjects that are not compliant with the study medication or study procedures may or may not be withdrawn according to the investigators discretion. Subjects that are noncompliant, but remain active in the study, will be followed so that an intent-to-treat analysis can be conducted. For safety variables, subjects will be analyzed with the treatment actually received (the safety population).

The primary analysis for the proposed study will be based on a standard intention-to-treat analysis with each study participant analyzed with respect to the randomized treatment assignment, regardless of eventual compliance. A secondary analysis may include imputation of missing data for select variables. A per-protocol analysis, disqualifying subjects or subject visits, might also be done, but is not planned because observational analyses of actual treatment use could introduce bias if the pattern of use is in some way related to the outcome.

Despite the randomized nature of the treatment assignments, in this relatively small sample of study subjects there may be imbalances with regard to potential confounding variables. Thus, as an initial step in the analysis, we will compare those assigned to Lotemax versus those randomized to the artificial tear with regard to demographic characteristics and potential confounding variables, using the non-parametric Wilcoxon rank sum test for continuous or ordinal variables, and chisquare or Fisher's exact tests for categorical variables.

The changes in primary end-points within each group during the course of treatment will be analyzed using Analysis of Variance (ANOVA) with post hoc analysis of Bonferroni correction. The values between the Lotemax and artificial tear groups will be compared with non-parametric Wilcoxon rank sum test. P values of 0.05 or less will be considered as statistically significant.

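### Entry requires a dendritic-cell count of at least 75/mm² and the qualifying image may be the baseline, so a within-arm fall in this primary endpoint is expected without any drug effect and cannot be read as efficacy

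*Combined protocol and SAP*

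**What the plan says.** All references are to the combined protocol and SAP.

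- **Entry rule.** Section 4.1 lists "Corneal dendritiform cell count by confocal microscopy of >=75/mm² (13 immune cells per image"). Section 4.2 excludes on "Central corneal subbasal dendritic cell count by *in vivo* confocal microscopy of" "<75/mm² in both eyes". However the inclusion list is read, the exclusion makes the threshold binding: at least one eye must reach 75/mm².
- **Baseline.** Section 7.1 says that standard-of-care confocal images from the screening visit, or within a week of it, "may be used to determine eligibility and as a baseline assessment". In the Section 7.8 schedule, the row beginning "In vivo confocal" is marked under Screening, Week 2 and Week 6, with no entry under Baseline. There is therefore one scheduled pre-treatment image.
- **Endpoint.** Section 10.1 includes among the primary endpoints "Corneal subbasal immune dendritiform cells: Density, size, and cell field". Section 10.3 uses density of these cells for the sample size.
- **Analysis.** Section 10.5 plans the within-group test as follows: "The changes in primary end-points within each group during the course of treatment will be analyzed using Analysis of Variance (ANOVA"), with Bonferroni post hoc tests. It then says: "The values between the Lotemax and artificial tear groups will be compared with non-parametric Wilcoxon rank sum test". One significance rule, P of 0.05 or less, covers both. The section does not say which of the two decides efficacy, which eye is analysed, or how selection on the baseline is handled.

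**The concern.** A baseline value that is kept because it was high is, on average, above that subject's usual level. The next measurement tends to be lower with no treatment at all. When the same image both admits the subject and serves as baseline, the expected change from baseline is negative, and the within-arm hypothesis of no change is false by design. A correctly specified repeated-measures ANOVA does not remove this, and neither does a Bonferroni correction. Both deal with variance and multiplicity, whereas the problem is that the expected change is not zero.

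What is at stake is interpretation. A significant fall in the Lotemax arm could be taken as efficacy, and one in the artificial-tear arm as benefit from the comparator. The pattern of significant in one arm but not in the other could be taken as a difference between treatments. The within-arm ANOVA is the only analysis in 10.5 that is expressly about change, and nothing there ranks it below the between-arm test.

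**Working it through.** **The plan's own figures.** The plan gives no figure for the expected within-arm change, so there is none to reproduce on this point. Section 10.3 supplies two inputs: SD 44 and 22 per group. (The printed formula gives 4 × 44² × 1.96² / 52² = 11.0, and 22 is twice that. That is a separate matter; 22 is used here only as the planned number per arm before the allowance for loss to follow-up.)

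**Inputs from the documents:** threshold 75/mm² in at least one eye (4.1, 4.2); one pre-treatment image and follow-up images at weeks 2 and 6 (7.5, 7.8); SD 44 (10.3); 22 per arm (10.3); significance level 0.05 (10.5).

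**Assumptions, not in the documents:** SD 44 applies before selection; values are normal; source-population mean μ is 50-100/mm²; visit-to-visit reliability R is 0.7-0.9; true values in the two eyes correlate 0.8; the ANOVA is a repeated-measures one; no drug effect.

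**Step 1, closed form for one eye selected and analysed.** Expected fall = (1 − R) × 44 × λ, with λ = φ(z) / (1 − Φ(z)) and z = (75 − μ) / 44.

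- μ = 50: 44λ = 52.4, so the fall is 15.7 at R = 0.7 and 5.2 at R = 0.9.
- μ = 75: 44λ = 35.1, so the fall is 10.5 and 3.5.
- μ = 100: 44λ = 20.9, so the fall is 6.3 and 2.1.

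**Step 2, simulation.** 2,000 trials per scenario, 22 per arm, three visits. Each cell gives the mean spurious fall (cells/mm²) and the within-arm ANOVA rejection rate.

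| μ | R | One eye selected and analysed | Mean of both eyes | Higher-count eye |
|---|---|---|---|---|
| 50 | 0.7 | 15.8; 61.8% | 6.8; 24.7% | 20.3; 84.7% |
| 50 | 0.9 | 5.3; 22.6% | 2.4; 11.7% | 7.9; 47.2% |
| 75 | 0.7 | 10.6; 31.2% | 4.2; 11.1% | 16.6; 67.6% |
| 75 | 0.9 | 3.5; 11.3% | 1.4; 7.2% | 6.6; 34.7% |
| 100 | 0.7 | 6.3; 12.0% | 2.0; 5.1% | 13.9; 50.9% |
| 100 | 0.9 | 2.1; 8.2% | 0.7; 5.4% | 5.7; 28.0% |

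The one-eye falls agree with Step 1. The simulation standard error of a rejection rate is at most √(0.25/2000) = 1.1 percentage points; a repeat of the higher-count column gave 27-86%. In that column part of the fall comes from picking the higher of two noisy readings rather than from the 75/mm² rule.

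**Step 3, Bonferroni.** The chance of a significant Bonferroni-corrected fall from baseline to week 6 over the same grid is 2.9-40.1% (one eye), 1.5-12.8% (mean of both eyes) and 14.2-67.0% (higher-count eye). With three comparisons and one direction, the nominal rate is 0.05 / 3 / 2 = 0.8%.

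**Step 4, the one-arm-only pattern.** At μ = 75, R = 0.7, one eye, and with independent arms, the chance of significance in the Lotemax arm but not in the tear arm is 0.312 × 0.688 = 21%. At a true 5% level it would be 0.05 × 0.95 = 4.8%.

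**Step 5, between arms.** Under the same selection and no drug effect, over wider ranges (R 0.5-0.95, μ 50-150, all three eye rules), the Wilcoxon test rejected in 3.6-5.9% of trials on change from baseline and 3.9-5.8% on week-6 values. That is nominal.

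**The case against.** The strongest reply is that the trial is already comparative. Section 2.1 sets Lotemax against the artificial tear, Section 8.2 describes effectiveness as a comparison of the two, and Section 10.5 bases its primary analysis on randomised assignment and plans a between-arm test. That test is unaffected by the selection. This stands, and it limits the point to interpretation of the within-arm tests. It does not answer the point: the intention-to-treat statement says how subjects are grouped, not which test decides, and 10.5 applies one significance rule to both analyses.

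The second reply is that the size is unknown. This also stands. The documents give no repeat-image reliability, source mean or analysed eye. Section 10.3 does not say that SD 44 describes unselected subjects. A normal model with mean 50 and SD 44 puts about 13% of counts below zero, so the top of the range is the least secure. Only one eye has to qualify, which dilutes the effect if both eyes are averaged; at a source mean of 100 the ANOVA is then close to nominal.

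A reader might infer more than this, in three ways:

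- **That the data will show a fall.** The documents support only an expected fall, of a size they do not fix.
- **That all the confocal primary endpoints are affected.** Selection acts directly on cell density. Other measures are affected only so far as their errors correlate with it.
- **That the comparison of Lotemax with artificial tears is biased.** Randomisation balances the effect, and Step 5 confirms this.

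**Conclusion.** The point holds for dendritic-cell density and for the within-arm tests only. Entry at 75/mm² or more, with the qualifying image allowed as baseline and no second pre-treatment image scheduled, means that a fall is expected in each arm without a drug effect whenever repeat images are not perfectly reliable and the threshold binds. A significant within-arm ANOVA for this endpoint therefore cannot be read as a treatment effect.

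Under the stated assumptions the size runs from negligible (mean of both eyes, reliable images, source mean well above 75) to large (higher-count eye, noisier images, low source mean). Which eye is analysed matters as much as the reliability. The conclusion that the within-arm test is uninterpretable as efficacy does not depend on where in the range the truth lies; the probability of being misled does. The randomised comparison remains valid, so this calls for a clarification before analysis and is not a flaw in the trial's comparative result.

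**What to change.** In Section 10.5:

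1. State that efficacy is concluded only from the randomised between-arm comparison, in line with the objective in Section 2.1.
2. Report within-arm changes descriptively, as estimates with intervals and no significance claim.
3. Add a note that within-arm change in dendritic-cell density includes regression to the mean from the 75/mm² entry rule.

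The change is wording only and needs no further images, visits or subjects. The cost is the loss of within-arm P values as claims of effect.

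Using a second pre-treatment image as baseline only for subjects who happen to have two is not recommended. It would mix two baseline definitions, leave single-image subjects as they are, and require a change to Section 7.1.

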2. STUDY OBJECTIVES

2.1 Primary Objective

To evaluate the efficacy of Lotemax as compared to Artificial Tear over a period of 6 weeks, using clinical and in vivo confocal microscopic findings.

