3.2.3 Breaking the Mask

A subject's medication may be unmasked at any point for a medical emergency or to supplement a serious adverse event (SAE) report. The subjects will be unmasked at the end of the study in order to provide optimal ongoing care.

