8.2 Effectiveness Assessments

Comparison of the efficacy of the taper Lotemax versus artificial tear will be evaluated using both clinical and IVCM parameters which include the followings:

Ocular Signs

- Corneal epitheliopathy (corneal fluorescein staining using the NEI grading scheme). (Appendix IV)
- Conjunctival epitheliopathy (conjunctival lissamine green staining using NEI grading scheme). (Appendix IV)
- > Tear Film Break Up Time (TBUT)
- Schirmer's Test with Anesthesia

Ocular Symptoms

- Ocular Surface Disease Index (OSDI) questionnaire. (Appendix II)
- > Symptom Assessment iN Dry Eye (SANDE) questionnaire. (Appendix III)

In Vivo Confocal Microscopy

- > Superficial corneal epithelial cells: Density, size, and hypereflectivity
- > Corneal subbasal immune dendritiform cells: Density, size, and cell field
- > Corneal subbasal nerves: Number and length of the total, main nerves and the branches

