10.3 Sample Size Determination

To calculate sample size, density of sub-basal dendritic cells in the central cornea was used as an outcome measure. Based on a previous published paper (Villani et al, Innate Immunity. 2013;19(4) 420–427), a difference of 52 cell/mm² with a standard deviation of 44 were used to calculate the sample size with the following formula:¹⁻³ $4 \times \sigma^2 \times Z(1 - \alpha/2)^2$

$$N = \frac{4 \times \sigma^2 \times Z(1 - \alpha/2)^2}{d^2}$$

With $\alpha = 0.05$ ($Z_{\alpha} = 1.96$), d = 52, and p = 44, a sample size of 22 was calculated for each group (44 for both groups). To compensate for potential loss to follow-up, a total of 50 subjects will be enrolled in this study.

- 1) Daniel WW. Biostatistics: a foundation for analysis in the health sciences 7th ed. New York, NY: Wiley, 1999; 180-185, 268–270.
- 3) Eng G. Sample size estimation: how many individuals should be studied? Radiology. 2003; 227:309-13.

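### Section 10.5 compares undefined values between arms by an unadjusted Wilcoxon test; it should fix visit and scale, adjust for baseline density and report an estimate with a confidence interval

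*Combined protocol and SAP*

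**What the plan says.** The question is between arms. The objective in section 2.1 is "To evaluate the efficacy of Lotemax as compared to Artificial Tear over a period of 6 weeks", and section 8.2 says "Comparison of the efficacy of the taper Lotemax versus artificial tear will be evaluated using both clinical and IVCM parameters". Section 10.5 answers it with one sentence: "The values between the Lotemax and artificial tear groups will be compared with non-parametric Wilcoxon rank sum test". A p-value of 0.05 or less counts as significant.

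The sentence just before concerns each arm separately: "The changes in primary end-points within each group during the course of treatment will be analyzed using Analysis of Variance (ANOVA"), with Bonferroni post hoc comparisons. That correction belongs to the within-arm analysis only.

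Other relevant text:
- Section 10.1 lists the confocal parameters with no visit and no level-or-change definition.
- Section 7.5 schedules follow-up at weeks 2 and 6.
- Section 10.3 sizes the trial on one outcome: "density of sub-basal dendritic cells in the central cornea was used as an outcome measure".
- Section 7.8 schedules confocal microscopy at screening. Section 4.2 excludes subjects whose density is "<75/mm² in both eyes", and section 7.1 says that standard-of-care images "may be used to determine eligibility and as a baseline assessment".
- Section 10.5 expects chance imbalances in a small sample and tests for them, but no adjustment follows.
- Section 5.2 keeps a subject who has imaging at two of the three visits.
- Section 3.2.3 says "The subjects will be unmasked at the end of the study in order to provide optimal ongoing care".

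**The concern.** The text allows at least four versions of the between-arm test on dendritic-cell density: level or change, at week 2 or week 6. Nothing in section 10.5 binds the analyst to one of them, and no multiplicity correction applies across them. A version chosen with the data in view no longer has a 5% error rate.

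The planned output is also thin. A rank sum p-value gives no size of effect in cells/mm² and no interval around it. Baseline density is available for subjects entering the trial and is likely to predict follow-up density, but only a change-score reading would use it, and then not as an adjustment.

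**Working it through.** **1. The plan's own figure.** Section 10.3 uses SD 44 and difference 52. The printed formula gives 4 × 44² × 1.96² / 52² = 11.0, whereas the plan states 22 per group, which appears only if the result is doubled. That is a separate matter. The checks below take 22 per group as planned.

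**2. Is the quantity fixed anywhere?** Set side by side:

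| Section | Visit | Level or change |
|---|---|---|
| 1.2 | during the 6-week regimen | changes |
| 2.1 | over 6 weeks | not stated |
| 7.5 | weeks 2 and 6 | not stated |
| 10.1 | not stated | not stated |
| 10.5, within arm | course of treatment | changes |
| 10.5, between arms | not stated | *values* |

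The background leans to change over six weeks. The analysis section does not say so, and its wording moves from changes to values.

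**3. Error rate if the version is left open.** Suppose success is claimed whenever any version reaches 0.05. For two-sided, approximately normal tests, k versions cannot exceed 1 − 0.95^k, which is 9.75% for k = 2 and 18.5% for k = 4. The versions share data, so the actual figures are lower.

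Simulation used assumptions that are not in the documents: SD 44 per eye, source mean 50–100 cells/mm², correlation over time 0.5–0.7, inter-eye correlation 0.5–0.8, mean of two eyes, at least one eye at 75 or more, 22 per arm. It was run with normal and with skewed (gamma) densities.
- Any one fixed version: about 5%.
- Week-6 level or change: up to about 8–10%.
- Week 2 also open: about 14–17%.

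**4. What adjustment does, in closed form.** Take SD 44 as the subject-level SD, r as the baseline-to-follow-up correlation, and ignore the entry threshold. The SD of a change is 44√(2(1 − r)), and the adjusted SD is 44√(1 − r²). The 95% half-width is 1.96 × SD × √(2/22).

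| r (assumed) | Level: SD, half-width | Change: SD, half-width | Adjusted: SD, half-width |
|---|---|---|---|
| 0.3 | 44.0, 26.0 | 52.1, 30.8 | 42.0, 24.8 |
| 0.5 | 44.0, 26.0 | 44.0, 26.0 | 38.1, 22.5 |
| 0.7 | 44.0, 26.0 | 34.1, 20.1 | 31.4, 18.6 |

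The choice between level and change therefore alters precision in either direction. Adjustment is at least as precise as both at every r shown.

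**5. Power, from the simulation with the entry threshold.** At 52, the unadjusted week-6 test and ANCOVA both have about 98% power or more. At 26 (half the planned difference, an assumption), ANCOVA gains over the week-6 Wilcoxon test about 3–4 points at r = 0.3, 5–11 at 0.5 and 12–23 at 0.7. ANCOVA's type I error stayed at about 4.5–5.5% in both the normal and the skewed models.

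**6. Within-arm change.** Subjects enter on high density in at least one eye, and the same images may serve as baseline. Under these assumptions an inert arm falls by 3–21 cells/mm² (normal) or 3–27 (gamma) from selection alone. A within-arm fall is therefore not evidence of a drug effect.

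**The case against.** The strongest reply is that the intended reading is clear enough: section 1.2 speaks of changes during a 6-week regimen against the artificial tear, section 2.1 gives six weeks, and the sentence before the test concerns changes. On that reading the comparison is change to week 6, which already uses baseline. This stands as the likeliest intention, and it makes four equally open versions a worst case. It does not close the gap, because the rule must be inferred and there would still be no estimate, interval or adjustment.

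Second, ANCOVA is a choice rather than a necessity. This stands too: at the planned difference it adds almost nothing, and the gain at 26 rests on assumed correlations.

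Third, averaging the eyes has a risk. Section 4.2 excludes only when both eyes are low, so one eye may start below 75/mm². If only eyes at or above 75 responded (an assumption), ANCOVA power at 26 would fall from 63–87% to 38–72% for correlations of 0.5–0.7. The eye rule therefore has to be chosen deliberately.

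Stronger conclusions that a reader might draw are not supported:
- *The error rate doubles or triples.* Only if someone selects the version on the results; nothing says that the sponsor will.
- *Analysis follows unmasking.* Section 3.2.3 unmasks for ongoing care and does not place that before the analysis. Section 3.2.2 masks the image analysts.
- *Regression to the mean biases the randomised test.* It affects both arms alike.

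**Conclusion.** The point holds as an inexpensive improvement. Section 10.5 leaves the visit and scale of the between-arm test unstated, makes no adjustment for baseline density, and plans no effect size or interval. The Wilcoxon test is not invalid: any single version named in advance keeps its 5% level.

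The exposure for dendritic-cell density is at most about 8–10% with week-6 level or change open, and 14–17% with week 2 open as well. Both figures suppose selective choice and the assumed correlations. The benefit of adjustment is mainly precision. Its power gain is negligible at 52 and modest to useful at 26, depending on a correlation that the documents do not give. Nor do they say whether the SD of 44 is per eye, per subject or of a change.

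**What to change.** Amend section 10.5, before any unmasked analysis, to state the following:
- The deciding comparison for dendritic-cell density, the sample-size outcome, is week-6 density, one value per subject, adjusted for baseline density by ANCOVA. It is reported as the difference in cells/mm² with a 95% CI. If skewness is expected, name rank-ANCOVA instead, and settle that choice before assignments are known.
- The Wilcoxon test on change to week 6 is the sensitivity analysis.
- Week 2 is secondary, and the within-arm ANOVA is descriptive.
- How the two eyes are combined, given that one may be below 75/mm² at baseline.
- How a missing week-6 image is handled, since section 5.2 tolerates one missed imaging visit while section 10.5 promises an intention-to-treat analysis.

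If the unadjusted Wilcoxon test is preferred as the deciding test, the minimum is to fix its visit and scale and add an estimate with CI, such as a Hodges–Lehmann shift.

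The cost is wording: no new visit, subject or measurement. The small downside is one added model assumption, which the rank-based sensitivity analysis covers.

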7.5 Follow-up Procedures

After enrollment, the subjects will be scheduled for a second visit (Week 2 ± 3 days) and a third visit (Week 6 ± 1 week).

The following procedures will be performed at all follow-up visits:

- Eye examination (best corrected visual acuity, bio-microscopy, applanation tonometry, funduscopy)
- Tear Break-up Time
- Corneal fluorescein staining
- Conjunctival lissamine green staining
- Schirmer's Test with anesthesia
- Ocular Surface Disease Index questionnaire
- Symptom Assessment in Dry Eye (SANDE) questionnaire

• Central Cornea In Vivo Confocal Microscopy

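### Ten unranked confocal measures are all primary, and the between-group tests at P ≤ 0.05 have no lead measure, no set visit and no multiplicity adjustment

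*Combined protocol and SAP*

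**What the plan says.** Section 10.1 lists the primary outcomes under three headings, with no order among them:

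- "Superficial corneal epithelial cells: Density, size, and hypereflectivity" (three measures)
- "Corneal subbasal immune dendritiform cells: Density, size, and cell field" (three measures)
- for the subbasal nerves, "Number and length of the main nerves and the branches" (four measures: two quantities for each of two nerve types)

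That makes ten. Section 8.2 gives the nerve item as "Number and length of the total, main nerves and the branches", which would raise the count to twelve.

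Section 10.5 sets out two analyses. Changes within each group "will be analyzed using Analysis of Variance (ANOVA) with post hoc analysis of Bonferroni correction". The randomised comparison comes in a separate sentence: "The values between the Lotemax and artificial tear groups will be compared with non-parametric Wilcoxon rank sum test". The threshold follows: "P values of 0.05 or less will be considered as statistically significant".

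On timing, section 7.5 introduces its list of assessments, which includes IVCM, with "The following procedures will be performed at all follow-up visits"; those visits are Week 2 and Week 6. Section 10.3 sizes the trial on central sub-basal dendritic-cell density. Sections 2.2, 10.4 and 10.7 are marked not applicable and add nothing on this point.

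**The concern.** Section 2.1 asks whether Lotemax is more effective than the artificial tear, so the between-group comparison carries the primary claim. That comparison may be run on ten co-equal measures, at one or two visits, each at the 5% level. No written rule says which result decides the question. The Bonferroni correction sits in the within-group sentence and does not reach the between-group test.

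If whichever measure reached P ≤ 0.05 were reported as a positive primary result, the error rate of that claim would be well above 5%. A lone P = 0.03 on one of the ten could not be read at its face value. Only a P value below 0.005 would survive Bonferroni over ten tests. A rule chosen after unmasking could not repair this credibly.

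**Working it through.** **Inputs from the documents.** Per-test level 0.05, two-sided (10.3 uses Z = 1.96). Primary measures 3 + 3 + 4 = 10 (10.1). Alternative counts: 12 with total nerves added (8.2), or 8 if the nerve item is read as two measures (3 + 3 + 2). Two follow-up visits with IVCM (7.5). For power: difference 52 cells/mm², SD 44, 22 per group, 50 enrolled (10.3), allocation 1:1 (3.2.1).

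**The plan's own figures.** The plan states no family-wise error rate, so there is none to reproduce. Its one related figure is 22 per group. The formula printed in 10.3 gives 4 × 44² × 1.96² / 52² = 11.0, not 22. That is a separate matter and does not enter the error-rate calculation; 22 per group is taken as given for power.

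**Error rate, independent tests.** The chance of at least one P ≤ 0.05 when nothing differs is 1 − 0.95^k:

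- k = 8: 33.7%
- k = 10: 40.1%
- k = 12: 46.0%
- k = 20 (ten measures at both visits): 64.2%

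**Error rate, correlated tests.** The documents give no correlations, so a range is assumed. With k normal test statistics sharing one pairwise correlation ρ and c = 1.96, the rate is

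1 − ∫ φ(u) [Φ((c − √ρ·u)/√(1−ρ)) − Φ((−c − √ρ·u)/√(1−ρ))]^k du,

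evaluated numerically:

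| Tests | independent | ρ = 0.3 | ρ = 0.5 | ρ = 0.7 | ρ = 0.9 |
|---|---|---|---|---|---|
| 8, one visit | 33.7% | 30.0% | 25.0% | 19.1% | 11.9% |
| 10, one visit | 40.1% | 35.1% | 28.7% | 21.3% | 12.8% |
| 12, one visit | 46.0% | 39.7% | 31.9% | 23.2% | 13.5% |
| 20, two visits | 64.2% | 54.0% | 41.9% | 29.0% | 15.5% |

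The last row treats all twenty tests as equally correlated, so a measure is no closer to itself at the other visit than to a different measure. If the correlation between visits is instead set at 0.5 (also an assumption), the two-visit rates at ρ = 0.3, 0.5, 0.7 and 0.9 between measures are about 55%, 46%, 36% and 22%.

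**Check with the planned test.** Simulated Wilcoxon rank sum tests on ten measures, 22 per group, 10,000 trials per setting, gave 39.8% (independent), 35.8% (0.3), 29.8% (0.5) and 13.6% (0.9), in line with the ten-test row.

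**Power for dendritic-cell density.** The noncentrality is (52/44) × √(22/2) = 3.92 with 22 per group and (52/44) × √(25/2) = 4.18 with 25. Each cell gives the noncentral-t result, then the simulated Wilcoxon result on normal data:

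| Per-test level | 22 per group | 25 per group |
|---|---|---|
| 0.05 (single primary) | 96.9% / 96.1% | not needed |
| 0.005 (ten tests) | 82.3% / 77.8% | 88.5% / 85.4% |
| 0.0025 (twenty tests) | 75.2% / 69.5% | 83.0% / 78.8% |

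**The case against.** The strongest reply is that the plan already points to a lead measure and a visit. Dendritic-cell density is the only IVCM measure with an effect size and SD (10.3) and the only one used for eligibility (4.1 and 4.2, threshold 75/mm²). Sections 1.2 and 2.1 speak of a six-week course, which favours Week 6. A sympathetic reader could infer density at Week 6. These are hints, though, and not a rule: 10.3 treats density as one outcome among others, 10.1 gives it no priority, and the six-week wording does not fix a test visit. If this was the intention, writing it down is the fix.

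A second reply is that the plan never says one significant result out of ten counts as success. In a single-site study of 50 subjects, the tests could be read one by one as mechanistic findings, each at its own 5% level. It is true that the 13–40% range applies only if any significant measure may carry the claim. But the documents describe a randomised, double-masked efficacy trial with designated primary endpoints and a significance threshold, and nothing excludes that reading.

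Third, the correlations are assumed, and a uniform 0.9 across epithelial, immune-cell and nerve measures has no support in the documents. This stands. It weakens the 13% end of the range, and lower correlations give higher rates. The two-visit figures also depend on the correlation model; the alternative shown above raises them.

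Finally, the power figures rest on a difference and SD taken from a cited paper and on a group size that the printed formula does not yield. They show the relative cost of the options and do not guarantee power.

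**Conclusion.** The concern holds. The primary efficacy claim has no decision rule that controls its error at 5%. Read as ten measures at one visit, with any significant result able to carry the claim and no true difference on any measure, the false-positive chance is 40.1% under independence and about 35% to 13% at assumed equal correlations of 0.3 to 0.9. Counting eight or twelve measures, or testing both visits, changes the figure but never brings it to 5%; the lowest value in the table is 11.9%. This needs correcting before unmasking.

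**What to change.** **Preferred.** In 10.1, name central corneal sub-basal dendritic-cell density at Week 6 as the single primary endpoint, and in 10.5 test it between groups at two-sided 0.05. Make the other nine IVCM measures and all Week 2 comparisons secondary with a Holm adjustment, or label them exploratory. Reword 2.1 to match, since it now rests the primary objective on clinical and IVCM findings together, and reconcile the nerve lists in 8.2 and 10.1. The investigators may prefer another single measure, but density is the only one for which the documents support a power statement. The cost is wording only: no added subjects, nine measures lose primary status, and power is about 97% (t-test) or 96% (Wilcoxon) at 22 per group.

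**If all ten must stay primary.** Fix one analysis visit in 10.5 and apply Holm or Bonferroni across the ten (0.005 at the first step). Bonferroni power for density is then about 82% or 78% at 22 per group, or 88% or 85% if all 25 per group are evaluable; Holm does at least as well.

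**If both visits are to be tested.** Adjust across all twenty tests (0.0025 at the first step). Bonferroni power is about 75% or 69% at 22 per group, or 83% or 79% at 25.

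Power for the other nine measures is unknown under any option, because the documents give no effect size or SD for them.
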